Study Protocol - Study Group

Study Group Document

Protocol ID: FBU-[name]-001

Date: September 12, 2025

Study Group

To determine the number of participants to be included in the study, a power analysis was conducted.

The test power was calculated using the G*Power 3.1 program.

In a similar study conducted by Huang et al. (2020), the effect size regarding changes in knowledge level

was calculated as 0.928. In order to achieve a statistical power above 95%; at a 5% significance level and

an effect size of 0.928, a total of 24 participants per group are required (df=23; $t=2.069$).

Considering possible attrition and to ensure high statistical power, the study aimed to recruit 29 participants.

Statistical Analysis of Data

The data obtained in the study will be analyzed using SPSS (Statistical Package for Social Sciences) for Windows 22.0.

The Kolmogorov-Smirnov test will be used to determine whether the data are normally distributed.

According to the Kolmogorov-Smirnov test, if $p > 0.05$, the distribution is considered normal.

If $p < 0.05$, the distribution is considered non-normal, and skewness and kurtosis values will be examined.

If the skewness and kurtosis values are between +2 and -2, the variable is considered to have a normal distribution (George & Mallery, 2010).

Changes related to repeated measurements will be analyzed using repeated measures ANOVA if the data are normally distributed,

or the Friedman test if the data are not normally distributed.

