Appendix – Output Screenshot

t tests - Means: Difference between two dependent means (matched pairs)

Analysis: A priori: Compute required sample size

Input: Tails = Two

Effect size dz = 0.9284596

α err prob = 0.05

Power (1- β err prob) = 0.99

Output: Noncentrality parameter δ = 4.5485045

Critical t = 2.0686576

Df = 23

Total sample size = 24

Actual power = 0.9916119

References

George, D., & Mallory, M. (2010). SPSS for Windows Step by Step: A Simple Guide and Reference, 17.0 update (10th ed.). Boston: Pearson.

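### Does stating power above 95% for 24 participants, when the appended run targeted 99%, call for a change to the sample-size statement?

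*Protocol*

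**What the plan says.** The Study Group section of the Protocol takes an effect size of 0.928 from a similar published study. It then gives the aim, "In order to achieve a statistical power above 95%; at a 5% significance level and" that effect size, and concludes that "a total of 24 participants per group are required", citing 23 degrees of freedom and a critical t of 2.069. It sets recruitment at 29 to allow for attrition and to keep power high.

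The Appendix (Output Screenshot) shows the a priori run for a matched-pairs t-test. Its inputs are "Input: Tails = Two", "Effect size dz = 0.9284596", "α err prob = 0.05" and "Power (1- β err prob) = 0.99". Its results are 23 degrees of freedom, a critical t of 2.0686576, a noncentrality parameter of 4.5485045, "Total sample size = 24" and "Actual power = 0.9916119".

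The effect size, degrees of freedom, critical t and the number 24 agree between the two places, so the text is reporting this run. The power threshold is expressed differently: above 95% in the text, 0.99 in the output.

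**The concern.** A sample-size justification should be reproducible from the inputs it states. An a priori calculation returns the smallest number that meets its target, so a reader who sees that 24 are required for power above 95% expects 24 to be the minimum for that threshold. Someone who enters 0.928, 5% two-sided and 95% into a paired t-test gets 18. The reader may then suspect an arithmetic error or a different test. The sentence in the Study Group section is also the only place in the body text that states the design power.

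If the mismatch had run the other way, with a higher power claimed than the run delivered, the trial would have been smaller than its stated aim needed. That is what would be at stake, so the direction and size of the discrepancy have to be checked.

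**Working it through.** **Inputs.** From the Appendix: two-sided paired t-test, α = 0.05, dz = 0.9284596, target power 0.99. From the Study Group section: effect size 0.928 (rounded), power above 95%, recruitment of 29.

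**Formulas.** For n pairs:

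- df = n − 1
- noncentrality δ = dz × √n
- critical value c = the 0.975 quantile of t with df degrees of freedom
- power = 1 − F(c; df, δ) + F(−c; df, δ), where F is the noncentral t distribution function

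**Step 1: reproduce the Appendix at n = 24.** df = 23; c = 2.0686576; δ = 0.9284596 × √24 = 4.5485045; power = 0.9916119. Every printed result is matched.

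**Step 2: power at other sample sizes.**

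| n | Power, dz = 0.9284596 | Power, dz = 0.928 |
|---|---|---|
| 17 | 0.9484 | 0.9482 |
| 18 | 0.9598 | 0.9596 |
| 23 | 0.9890 | 0.98896 |
| 24 | 0.9916 | 0.99156 |
| 29 | 0.9979 | 0.9979 |

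The smallest n with at least 95% power is 18. The smallest n with at least 99% power is 24. Rounding the effect size to 0.928 changes neither, so rounding does not explain the difference.

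**Step 3: could another 95% calculation give 24?** A one-sided paired test needs 15 for 95% (20 for 99%). A comparison of two independent groups with a standardised difference of 0.928 needs 32 per group for 95% (44 per group for 99%). None of the variants tried at 95% gives 24. The number comes from the two-sided paired run at 99%.

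**Step 4: compare the claim with the result.** The text promises power above 95%. The run delivers 0.9916119 at n = 24, which exceeds that bound by 0.9916 − 0.95 = 0.0416, about 4 percentage points. The excess over the 95% minimum is 24 − 18 = 6 participants.

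**The case for a change.** The strongest case for a change rests on the word required. In an a priori calculation it means the minimum, and on that meaning 24 is not the requirement for the threshold named, because every n from 18 to 23 also exceeds 95%. The body text never mentions 99%, so the calculation cannot be repeated from that paragraph alone. Printing the target in an appendix leaves two power figures for one calculation, and one clause would remove the discrepancy.

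The arithmetic in that argument is right, and the wording is imprecise. The argument does not show a wrong figure. The text does not say 95% power; it gives a lower bound, and both the 0.99 target and the 0.9916 reached satisfy it. The document is short, and the Appendix directly follows the text and lists every input. The degrees of freedom and critical t quoted in the text lead straight to that run, so a reader who gets 18 can find the reason at once.

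A full rewrite of the sentence also has a drawback. The same sentence speaks of 24 per group where the output gives a total of 24. Any rewording that chose one of these, or that confirmed recruitment at 29, would settle a more consequential question in passing. That question needs its own reconciliation by the sponsor.

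**Conclusion.** No change is needed on this point. The Study Group section understates the power target of its own run (above 95% against 99%), but what it says about the power reached is true, and the target is disclosed in the Appendix. The discrepancy is conservative: 24 participants give 0.9916, against 0.9598 at the 18 that would just exceed 95%. Naming 99% in the text would be a harmless editorial clarification. It would leave the required number, the recruitment figure and the analysis as they are.

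This holds on the protocol's own sizing assumptions: one sample, a two-sided paired t-test at 5%, and dz = 0.928. The figure of 18 only locates the mismatch. It is not a tolerable number of completers, because the Protocol plans repeated measures ANOVA or the Friedman test and not a paired t-test. The conclusion also does not cover the conflict between a per-group and a total count. If two independent groups were meant and 0.928 were the difference between them (an assumption the document does not settle), 24 per group would give power of about 0.88. That would be a separate matter of design, and restating the power target would not resolve it.

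### The normality screen that picks repeated measures ANOVA or Friedman reads as a check of the scores, but both tests use only within-person differences, so the check should be made on those

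*Protocol*

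**What the plan says.** The Statistical Analysis of Data section sets out a complete decision rule.

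- First step: "The Kolmogorov-Smirnov test will be used to determine whether the data are normally distributed". A p-value above 0.05 settles the matter as normal.
- Second step, reached only after a rejection: "If $p < 0.05$, the distribution is considered non-normal, and skewness and kurtosis values will be examined".
- Reversal: "If the skewness and kurtosis values are between +2 and -2, the variable is considered to have a normal distribution".
- Consequence of a normal label: "Changes related to repeated measurements will be analyzed using repeated measures ANOVA if the data are normally distributed". After a non-normal label, Friedman takes its place.

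Neither within-person differences nor model residuals are mentioned. The sample size, by contrast, is built on differences. The Appendix – Output Screenshot names the test as "Difference between two dependent means (matched pairs"), with "Effect size dz = 0.9284596" and "Actual power = 0.9916119".

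**The concern.** A normality check is useful for choosing a test only if it examines the quantity whose distribution matters to that test. Repeated measures ANOVA works on within-person contrasts, and Friedman works on ranks within each person. The spread of people's overall levels drops out of both. That spread does enter the skewness, kurtosis and Kolmogorov-Smirnov statistic of the scores.

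The screen can therefore err in two directions. Skewed levels with well-behaved changes can send an outcome to Friedman without need, which costs power. Badly behaved changes hidden under a roughly normal spread of levels can keep an outcome in ANOVA when the rank test would do better. In both cases the data decide whether the answer concerns means or ranks, partly on information that bears on neither.

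**Working it through.** **The plan's own figure.** Inputs from the Appendix: two-sided alpha 0.05, dz = 0.9284596, n = 24. Noncentrality = dz × √n = 0.9284596 × √24 = 4.5485. The critical t on 23 df is 2.0687. The noncentral t distribution gives power 0.9916, so the output reproduces. This is the power of a test on within-person differences.

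**Invariance.** Write the score of person i at time j as Y_ij = p_i + m_j + e_ij.

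- Difference: Y_ij − Y_ik = (m_j − m_k) + (e_ij − e_ik). The level p_i cancels.
- ANOVA: F = [n Σ_j (Ȳ.j − Ȳ..)² / (k−1)] / [Σ_ij (Y_ij − Ȳi. − Ȳ.j + Ȳ..)² / ((n−1)(k−1))]. Adding c_i to all of person i's scores moves Ȳi. by c_i, and moves Ȳ.j and Ȳ.. both by the mean of the c_i. Everything cancels, so F is unchanged.
- Friedman: Q = 12/(nk(k+1)) × Σ_j R_j² − 3n(k+1), where R_j is the sum over people of the within-person ranks at time j. The order within each person does not change, so neither does Q.
- Numerical check with 29 people, three times and a strongly skewed constant per person: F = 1.5637 before and after, Q = 2.6897 before and after.

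The label does change. In one simulated dataset with identical within-person changes, one set of person levels led to ANOVA with p = 0.022 and another led to Friedman with p = 0.115.

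**Size.** All of the following is assumed, because the protocol gives no distribution or number of measurements: one group, three measurements, a linear shift, Lilliefors critical values (0.176 at n = 24, 0.161 at n = 29), Greenhouse-Geisser ANOVA, Friedman with chi-square p, and every screened variable having to be called normal for ANOVA to be used. Power at n = 24, dz = 0.5, between-person share of variance 0.8:

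| Person levels / within-person errors | Screen on scores | Screen on differences |
|---|---|---|
| lognormal / normal | 0.49 | 0.54 |
| normal / exponential | 0.57 | 0.67 |
| normal / lognormal | 0.68 | 0.94 |

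In the first row the score screen sends 47% of datasets to Friedman, against about 2% for the difference screen. In the second row the figures are 4% and 37%. For lognormal levels with normal errors, over shares of 0.5 to 0.8, the score screen sends 22–47% to Friedman at n = 24 and 25–54% at n = 29, although the errors are exactly normal.

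At dz = 0.928 the gain from moving the screen is about 0.00 to 0.03. Type I error was about 3–5% with the score screen and 4.4–5.9% with the difference screen.

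**The Friedman branch on the Appendix inputs.** With two measurements Friedman is the sign test. For normal differences, P(difference > 0) = Φ(0.928) = 0.823. At n = 24, chi-square p rejects at 17 or more of 24, since (2×17 − 24)²/24 = 4.17 > 3.84; power is 0.952. Exact p needs 18 or more; power is 0.884. At n = 29 the figures are 0.977 and 0.943.

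**The case against.** **Raw scores are not named.** This stands as a matter of wording. The text speaks of the data and the variable, and which quantity is checked could be settled in an analysis plan. But the protocol writes a full rule, and anyone following it in the ordinary way would screen the scores. If differences were meant, one phrase would settle it.

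**The effect is small where it counts.** This also stands. The only effect size in the documents is 0.928, where the gain is at most about 0.03. The larger gains use dz = 0.5, which the documents do not mention. With uncorrected Kolmogorov-Smirnov p-values the first row's loss shrinks too: the score screen gives 0.52, against 0.54 for ANOVA throughout.

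**A single test fixed in advance would be cleaner.** A reader might infer that the rule should be deleted and ANOVA always used. The figures do not support that as a general remedy. With normal levels and exponential errors, always using ANOVA gives 0.56 against 0.57 for the current rule, so nothing is gained. With lognormal levels and errors (share 0.5) it gives 0.63 against 0.93. Fixing one test is a legitimate option, but a trade-off.

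**The ±2 step and the Friedman power.** The ±2 step can only overturn a rejection. At n = 29 it returned 45% of rejected exponential samples to normal, and it never examines samples that passed. It tilts the choice towards ANOVA, but no separate harm was shown. A reader might also infer that the Friedman branch misses the power stated under Study Group. In the two-measurement calculation that is so only with exact p-values; with chi-square p it stays above 95% at 24 and at 29. Both matters are secondary.

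**More than one group.** The Study Group section gives its sample size per group, which may suggest a between-group comparison. The only tests named are within-person, so the argument is unaffected.

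**Conclusion.** The point holds as a badly aimed check. The screen, read plainly, looks at scores, whereas both tests and the sample size calculation rest on within-person contrasts. The invariance is algebra and needs no assumption.

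The power differences do rest on assumptions: 0.05, 0.10 and 0.26 in the three rows above (0.54 − 0.49, 0.67 − 0.57, 0.94 − 0.68) at dz 0.5, and about 0.00 to 0.03 at the planned effect. In the cases simulated, the screen on differences matched or beat the screen on scores, apart from differences of about 0.001.

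Two stronger readings should be resisted. A data-driven choice of test might be thought to inflate false positives, but type I error stayed near or below 5–6% under either screen. Nor does this point show the study to be too small: the sample size calculation reproduces exactly and is not affected. This is an improvement worth making, of low priority.

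**What to change.** In Statistical Analysis of Data, state that the normality check is applied to the within-person differences between measurement times, or to the residuals of the repeated measures model, and not to the scores at each time. With more than two measurements, also say how the separate verdicts combine; the calculations above required every one to be called normal. Report the test that was not selected as a sensitivity analysis for every outcome.

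If the sponsor prefers a single primary test, it should be named before the data are seen, with the trade-off above in mind. If that test is a rank test, it needs its own power statement.

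The cost is a few sentences, one computed variable per pair of measurement times, and one extra reported test per outcome. Sample size and data collection do not change. What remains is that the data still choose between a test of means and a test of ranks; reporting both results makes that visible.

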Appendix – Output Screenshot

t tests - Means: Difference between two dependent means (matched pairs)

Analysis: A priori: Compute required sample size

Input: Tails = Two

Effect size dz = 0.9284596

α err prob = 0.05

Power (1- β err prob) = 0.99

Output: Noncentrality parameter δ = 4.5485045

Critical t = 2.0686576

Df = 23

Total sample size = 24

Actual power = 0.9916119

References

George, D., & Mallory, M. (2010). SPSS for Windows Step by Step: A Simple Guide and Reference, 17.0 update (10th ed.). Boston: Pearson.

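### Does a sample size computed for a paired t-test undermine the power claim when repeated measures ANOVA or Friedman is planned?

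*Protocol*

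**What the plan says.** The Appendix – Output Screenshot shows the calculation behind the sample size. It is for "t tests - Means: Difference between two dependent means (matched pairs", with "Input: Tails = Two", "α err prob = 0.05", "Effect size dz = 0.9284596" and "Power (1- β err prob) = 0.99". The output is 24 participants with actual power 0.9916119.

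The Study Group section attributes the 0.928 to a similar study's change in knowledge level. It claims power above 95% with 24 and sets recruitment at 29, to cover attrition and keep power high.

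The section Statistical Analysis of Data names different tests. Its first choice reads "Changes related to repeated measurements will be analyzed using repeated measures ANOVA if the data are normally distributed". The fallback that it names next is a rank test: "or the Friedman test if the data are not normally distributed". A variable goes to Friedman only if Kolmogorov-Smirnov gives p below 0.05 and skewness or kurtosis is then outside −2 to +2.

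The reference list describes the source of the effect size as a study of a mobile application "to improve central venous catheter care: A randomized controlled trial".

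**The concern.** A power figure should describe the test that will be reported. Here it belongs to a paired t-test that the analysis section never mentions, and neither planned test has a power figure of its own. Repeated measures ANOVA is close kin to the paired t-test. Friedman is not: it keeps only the within-person ranks, and with two measurements it reduces to the sign test. If it lost enough efficiency, the 24 completers called sufficient would have less than the stated power whenever the fallback was used.

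A second worry concerns the effect size. It comes from a randomised trial but is entered as a matched-pairs dz. A standardised mean difference d converts as dz = d/√(2(1−ρ)), so the two agree only at a pre-post correlation ρ of 0.5. A lower correlation would make the true dz, and the power, smaller in both branches.

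**Working it through.** **Inputs from the Appendix:** dz = 0.9284596, two-sided α = 0.05, n = 24.

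**1. The protocol's own figure.** Noncentrality δ = dz·√n = 0.9284596 × √24 = 4.5485. Critical t on 23 df = 2.0687. Noncentral-t power = 0.9916, an exact match. At n = 23 power is 0.9890, so 24 is the smallest n for 99%. At n = 18 power is 0.9598, so 24 holds 24 − 18 = 6 more than the claimed 95% requires under the paired test.

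**2. Repeated measures ANOVA, n = 24.** Assumptions: normal errors, compound symmetry, first-to-last difference equal to dz. With means expressed in units of the SD of the paired difference, the error variance is 1/2, so λ = n·Σ(μ−μ̄)²/(1/2).

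- Two times: λ = 24 × (0.9284596²/2) × 2 = 20.69 = δ². This is the paired t-test, power 0.992.
- Three times, linear change: λ is again 20.69, now on 2 and 46 df, power 0.982.
- Three or four times across linear and step patterns: 0.982 to 0.998.

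**3. Friedman with normal within-person errors, n = 24.** The protocol gives no number of times and no pattern, so these are assumed scenarios.

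| Scenario | Power |
|---|---|
| Two times, exact sign test, P(positive change) = Φ(0.9285) = 0.823 | 0.884 (true size 0.023) |
| Two times, chi-square version | 0.952 (true size 0.064) |
| Three times, linear change, chi-square version | 0.929 |
| Three times, step change, chi-square version | 0.978 |
| Four times, linear change, chi-square version | about 0.94 |
| Four times, step change, chi-square version | 0.983 |

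**4. Friedman with errors of the kind that lead to this branch, n = 24.**

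- Chi-square version, Laplace, t3, exponential or lognormal errors: 0.975 to 1.00.
- Exact version, two times: Laplace 0.942, exponential 0.965.

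**5. At 29 completers.** Chi-square Friedman is 0.962 or more with normal, heavy-tailed or skewed errors. The exact two-time version with normal errors is 0.943.

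**6. Effect size.** If 0.928 were a standardised mean difference (an assumption), paired-t power at n = 24 would be:

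| ρ | dz | Power |
|---|---|---|
| 0 | 0.66 | 0.87 |
| 0.2 | 0.73 | 0.93 |
| 0.27 | 0.77 | 0.950 |
| 0.3 | 0.78 | 0.96 |
| 0.5 | 0.93 | 0.992 |
| 0.7 | 1.20 | 0.9999 |

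Power drops under 95% only for ρ below about 0.27, and a correlation above 0.5 raises it beyond the stated figure.

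**The case for a change.** The best case for a change is that the normality rule is applied to the variable, not to within-person differences or residuals. Skewness between participants can then send the data to Friedman while the changes themselves stay normal, and the less favourable normal-error figures apply. A simulation with exponential between-person effects (SD 3) and normal errors (SD 1) put baseline skewness or kurtosis outside ±2 in about 36% of samples of 24, without applying the Kolmogorov-Smirnov step. Friedman power for linear change over three times was 0.928. Tied knowledge scores could lower it further.

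This stands as a possibility. It shows that power above 95% is unverified for Friedman, not that it fails: it needs one particular source of skewness together with a gradual change, and even then the gap is 0.95 − 0.928 = 0.022. Part of the 29 is reserved for attrition, so the margin in hand is less than five participants. That is fair too, but it does not make 29 too few.

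Light-tailed errors also hurt Friedman: two-peaked errors gave 0.895 with two times even at 29. But excess kurtosis in a population cannot fall below −2, so light tails alone would hardly send data to that branch.

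On the effect size, the protocol does not show how 0.928 was derived. But it describes it as an effect on change in knowledge, and an arm of a randomised trial has pre-post changes as well. Reading it as a between-group figure is a guess about a source that is not at hand.

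**Conclusion.** The power calculation and the analysis section name different tests, but nothing in the protocol shows the claim of power above 95% to be wrong. If 0.928 is a within-person dz, ANOVA gives 98% or more at 24 in the scenarios tried. Friedman gives about 88% to 98% with normal within-person errors, and about 94% or more (97% or more in the chi-square version) with the heavy-tailed or skewed errors tested. These figures assume independent, equal-variance errors within person and no ties.

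Sizing a short repeated-measures study on its main paired contrast is a common simplification, and here the run aimed at 99% while the text claims only 95%. Writing in a Friedman figure such as 93% would fix three measurements, linear change and normal errors in a plan that states none of these. Replacing Friedman with Wilcoxon signed-rank would matter only if there were exactly two measurements, which is also not stated; such detail may sit in an SAP that is not shown. The 24, the recruitment target of 29 and the conclusions would all stay as they are. This is missing detail with no gain from a change.
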